6.2. Superiority hypothesis

Sample size for superiority testing

During study planning, the hypotheses stating that BCD-085 Q4W and BCD-085 Q2W are superior to placebo ($H_{01}: \varepsilon_{2w} \leq \delta$, $H_{11}: \varepsilon_{2w} > \delta$; $H_{02}: \varepsilon_{4w} \leq \delta$, $H_{12}: \varepsilon_{4w} > \delta$, where ε_{2w} , ε_{4w} is the true difference in the rate of the efficacy variable between the arms treated with BCD-085 Q2W and with BCD-085 Q4W, respectively, δ is the superiority margin for BCD-085 over placebo) were tested with the following error values: type I error of 5% ($\alpha=0.05$), type II error of 20% ($\beta=0.2$), power of test of 80%. The efficacy endpoint used to calculate the sample size was PASI 75 rate by Week 12 in each arm [REDACTED]

The sample size needed to test the superiority hypotheses was calculated using the method described by [Chow Sh.-Ch., Shao J., Wang H., 2008]:

A horizontal bar chart consisting of 12 black bars of varying lengths. The bars are arranged in a single row, with their lengths increasing from left to right. The first few bars are relatively short, while the last few are significantly longer, with the longest bar on the far right extending almost to the edge of the frame.

Figure 1 consists of a 4x4 grid of 16 panels. Each panel contains a horizontal bar with a black segment on the left and a white segment on the right. The length of the black segment varies across the panels, representing different values of two parameters. The panels are labeled with their row and column indices:

- Panel (1,1) has a black segment from approximately x=0.0 to x=0.0.
- Panel (1,2) has a black segment from approximately x=0.0 to x=0.5.
- Panel (1,3) has a black segment from approximately x=0.0 to x=1.0.
- Panel (1,4) has a black segment from approximately x=0.0 to x=1.5.
- Panel (2,1) has a black segment from approximately x=0.5 to x=0.5.
- Panel (2,2) has a black segment from approximately x=0.5 to x=0.5.
- Panel (2,3) has a black segment from approximately x=0.5 to x=1.0.
- Panel (2,4) has a black segment from approximately x=0.5 to x=1.5.
- Panel (3,1) has a black segment from approximately x=1.0 to x=1.0.
- Panel (3,2) has a black segment from approximately x=1.0 to x=1.5.
- Panel (3,3) has a black segment from approximately x=1.0 to x=1.5.
- Panel (3,4) has a black segment from approximately x=1.0 to x=1.5.
- Panel (4,1) has a black segment from approximately x=1.5 to x=1.5.
- Panel (4,2) has a black segment from approximately x=1.5 to x=1.5.
- Panel (4,3) has a black segment from approximately x=1.5 to x=1.5.
- Panel (4,4) has a black segment from approximately x=1.5 to x=1.5.

The x-axis for each panel is labeled with a value from 0.0 to 1.5, and the y-axis is labeled with a value from 1 to 4.

[REDACTED]

[REDACTED]

[REDACTED]

Thus, the study should include at least 193 patients (77 in each BCD-085 arm and 39 in placebo arm). With a potential dropout rate of 10%, the study should involve 213 patients (85 patients in each BCD-085 arm and 43 patients in the placebo arm).

7. ANALYSIS POPULATIONS

Safety analysis

The safety analysis will include all patients randomized in the study (intent-to-treat (ITT) population).

Efficacy analysis

The efficacy will be assessed in the ITT (intent-to-treat) population, which includes all randomized patients. In addition, the efficacy can be evaluated in the PP (Per Protocol) population, which includes those patients who completed all visits without major protocol deviations.

Page 10 of 10

Immunogenicity analysis

The immunogenicity analysis will include all patients who have received at least one dose of BCD-085 and had an evaluable (not missing/lost/spoiled) serum sample taken before the first dose of BCD-085 and at least one evaluable (not missing/lost/spoiled) serum sample taken at subsequent visits.

Main demographics, baseline clinical and laboratory parameters obtained on the screening will be processed using descriptive statistics and will be analyzed in the efficacy and safety populations.

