### Safety analysis

The safety analysis will include all patients randomized in the study [intent-to-treat (ITT) population].

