**5.4.2. Follow-up of subjects who did not receive a single dose of the investigational product**

If the patient discontinues the study before getting the first dose of the investigational product, the investigator must fill out the End of Study Form in eCRF on the day of withdrawal. Non-dosed patients are followed-up only if they discontinue the study because of AEs/SAEs. In this case, the follow up is performed according to the study site standards.

If the subject discontinues the study before the first dose of the investigational product, his/her information will not be included in the safety analysis.

Translated from Russian to English, dated 26-Nov-2019

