### **8.2.2. Methods and timeframes for assessment and documenting of safety variables**

The safety analysis will include all patients who received at least one dose of the investigational product. Additionally, the SAE analysis will include all randomized patients starting from the ICF signing and until the end of their participation in the study.

Safety will be analyzed based on the information about

- AEs/SAEs,
- Physical examination data and vital signs,
- CBC, blood chemistry, and urinalysis results,
- ECG findings.

The frequency of these procedures is specified in section 4.6.1 “Schedule of study visits and procedures”. AEs/SAEs will be documented and reported in accordance with the Sponsor’s Manual.

The investigator is responsible for recording adverse events in the clinical study.

AEs are recorded beginning from the moment when the investigational product was injected the first time until the end of the follow-up period after the patient stopped taking the investigational product (as planned or prematurely). SAEs are recorded from the moment when the subject signed the informed consent form until the moment when he/she completed the study (as planned or prematurely). SAEs that were recorded during screening are not included in the total safety analysis. The Investigator can record an SAE later than stipulated by the Protocol if he/she believes that this SAE is related to the investigational product or study procedures.

An AE is considered to be resolved if the laboratory parameter, vital sign or symptom has returned to its baseline value. For all parameters, the baseline level is considered the value/sign severity that was seen in this patient before the first injection of BCD-085/placebo at the first scheduled visit per protocol. For AEs, including SAEs, of long-lasting/chronic nature, the resolution is the stabilization of the patient’s condition. For example, the AE “aggravation of chronic bronchitis” is considered to be resolved when the patient has achieved remission.

The Investigator must document non-serious AEs in the source documents and in the CRF, and show them to the Monitor at the next monitoring visit. Besides being recorded in the source documents and eCRF, serious adverse events (SAEs) must be reported to the Sponsor within 24 h in the SAE Report Form. SAE Report Forms must be sent to the Sponsor within 24 h by email to

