## **8.3 Requirements for reports, procedures for registration and reporting AEs, and filling out AE Report Forms**

### **8.3.1. Recording AEs/SAEs**

At every visit, a record should be made whether or not any AE occurred during the period from the previous visit. Any adverse event reported for a patient since he/she signed an informed consent form had to be recorded in source documents and in a special form for registration of adverse events (attachment to the CRF). AEs will be documented in accordance with the Sponsor's Manual.

AEs are recorded and numbered consecutively as they occur. Each AE is reported in an *AE Report Form*. Rules for documenting AE/SAE are described in detail in the Sponsor's Manual.

Adverse events must be recorded regardless of their seriousness and causal relationship with the study therapy. If an adverse event re-emerges, it should be recorded as a new AE and assigned a new number.

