## **9.8. Selection of subjects for analysis**

### **Safety analysis**

The safety analysis will include all patients randomized in the study.

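### The safety population is all randomized patients in SAP 7, Protocol 9.8 and the synopsis, but patients with at least one dose in Protocol 8.2.2 and 5.4.2; one set must be chosen.

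*SAP*

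**What the plan says.** Three places put every randomized patient in the safety analysis:

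- SAP 7: "The safety analysis will include all patients randomized in the study (intent-to-treat (ITT) population".
- Protocol synopsis, Safety analysis: "The safety analysis will include all patients randomized in the study [intent-to-treat (ITT) population".
- Protocol 9.8: "The safety analysis will include all patients randomized in the study", without the ITT label.

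Two places require dosing:

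- Protocol 8.2.2: "The safety analysis will include all patients who received at least one dose of the investigational product".
- Protocol 5.4.2: "If the subject discontinues the study before the first dose of the investigational product, his/her information will not be included in the safety analysis".

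Protocol 8.2.2 adds a separate rule for SAEs: "Additionally, the SAE analysis will include all randomized patients starting from the ICF signing and until the end of their participation in the study". The same section then leaves SAEs recorded during screening out of the total safety analysis, and 8.2.1 says they will be analysed separately.

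On timing, Protocol 8.1.1.1 does not count events before the first administration as AEs, and 8.2.2 starts AE recording at the first injection. Protocol 8.3.1 reads differently: "Any adverse event reported for a patient since he/she signed an informed consent form had to be recorded".

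SAP 10 states that the SAP does not depart from the Protocol's methods.

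**The concern.** The two definitions cannot both be followed when a randomized patient is never dosed. The Protocol expects that such patients may exist. Randomization closes the screening period, Protocol 4.6.1 allows up to 4 days from randomization to Visit 1, and 5.4.2 is written for patients who leave in that gap.

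A programmer working from SAP 7 would count these patients as free of AEs. A programmer working from Protocol 8.2.2 would leave them out. The set supplies the denominator for the proportions with AEs, grade 3/4 AEs, injection site reactions and discontinuations due to AEs. SAP 5 plans a final report and three supplementary reports, and comparing the safety of Q4W with Q2W is a stated objective. With the rule left open, the denominator could be settled after treatment is unblinded at Week 12.

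**Working it through.** The plan gives no figure to reproduce here. The check compares the texts and then sizes the effect.

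**Texts side by side**

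| Place | Who is in the safety analysis | An undosed randomized patient is |
|---|---|---|
| SAP 7 | all randomized (ITT) | in |
| Protocol synopsis | all randomized (ITT) | in |
| Protocol 9.8 | all randomized | in |
| Protocol 8.2.2, main rule | at least one dose | out |
| Protocol 5.4.2 | leaves out those who stop before the first dose | out |
| Protocol 8.2.2, SAE rule | all randomized, SAEs only | in, for SAEs |

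No section says which rule prevails.

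**Direction.** Let N be the number randomized to an arm, u the number never dosed and x the number of dosed patients with an AE. By Protocol 8.1.1.1 and 8.2.2 an undosed patient cannot add to x. The at-least-one-dose rule gives x/(N − u) and the all-randomized rule gives x/N. Since N ≥ N − u, the second is never larger.

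**Size.** If p is the proportion among dosed patients, the all-randomized figure is p × (N − u)/N, which is lower by p × u/N.

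Inputs:

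- N = 43 (placebo) and N = 85 (each BCD-085 arm): planned sizes, Protocol 9.3.2 and SAP 6.2.
- p = 39% (placebo) and 25% (120 mg): rounded from 11/28 = 39.29% and 7/28 = 25.00% in Protocol Table 13, Phase II psoriasis study. They serve only as an illustration.
- u: not given in the documents. The values 0, 1 and 2 are assumptions.

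| u | Placebo arm, N = 43 | BCD-085 arm, N = 85 |
|---|---|---|
| 0 | 39.0% | 25.0% |
| 1 | 0.39 × 42/43 = 38.1% | 0.25 × 84/85 = 24.7% |
| 2 | 0.39 × 41/43 = 37.2% | 0.25 × 83/85 = 24.4% |

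Each further undosed patient takes off 0.39/43 = 0.9 points in the placebo arm and 0.25/85 = 0.3 points in a BCD-085 arm.

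**Is 1 to 2 plausible?** Protocol 1.3.2.2.2.1 reports 120 patients in the Phase II psoriasis study and 117 in its safety analysis, a gap of 3/120 = 2.5%. The reason is not stated, so this is only a loose guide. The same share here would be 0.025 × 43 = 1.1 and 0.025 × 85 = 2.1 patients.

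**The case against.** The strongest case on the other side is that the SAP does follow the Protocol. SAP 7 matches Protocol 9.8, the statistics section on analysis populations, and the synopsis. The conflict begins inside the Protocol, and its effect is a point or two at most on the assumed numbers, with no bearing on the PASI 75 analysis. All of this stands. It makes SAP 10 incomplete rather than plainly false: the SAP agrees with one part of the Protocol and disagrees with 8.2.2 and 5.4.2, without saying so.

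A reader might infer more than the documents support:

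- **That pre-dose events would enter the AE proportions.** Protocol 8.3.1 invites this, and 5.4.2 also speaks of AEs in undosed patients. But 8.3.1 is a recording rule. Section 8.1.1.1 does not count pre-dose occurrences as AEs, 8.2.1 analyses screening SAEs separately, 8.2.2 leaves them out of the total safety analysis, and a footnote to Table 25 limits screening records to SAEs. The wording of 8.3.1 should be aligned, but it does not change the analysis.
- **That every safety endpoint is affected.** Protocol 8.2.2 deliberately uses all randomized patients for SAEs. The exposure-adjusted rate covers the extension, which an undosed patient cannot reach.
- **That safety will be tabulated by randomized arm whatever was given.** The ITT label suggests this, but the population texts say who is included, not how a misdosed patient is grouped.

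**Conclusion.** The conflict is real and should be corrected. SAP 7, as written, breaks the rule in Protocol 5.4.2 that for an undosed patient "his/her information will not be included in the safety analysis", and it counts that patient as AE-free.

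The likely size is below 2 percentage points in the placebo arm (0.9 to 1.8) and below 1 point in a BCD-085 arm (0.3 to 0.6). This assumes 1 to 2 undosed patients per arm, Phase II AE rates and the planned arm sizes. If every randomized patient is dosed, the two sets coincide and nothing changes. The downward direction rests on the first-dose start of AEs in Protocol 8.1.1.1 and 8.2.2.

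No efficacy conclusion is affected.

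**What to change.** - In SAP 7, Protocol 9.8 and the synopsis, define the safety set as all randomized patients who received at least one dose of BCD-085 or placebo. This matches Protocol 8.2.2 and 5.4.2.
- Keep the all-randomized SAE analysis of 8.2.2 as a separate listing, with SAEs before the first dose reported apart from the total safety analysis, as 8.2.1 and 8.2.2 already say.
- Align the AE start wording in 8.3.1 with 8.1.1.1 and 8.2.2.
- If patients are to be grouped by treatment received, state the rule by period, because Arm 3 moves to BCD-085 at Week 12 and Arms 1 and 2 share the Q4W schedule from Week 14. For Weeks 0 to 12, group by the regimen received. After Week 12, group by original arm, with Arm 3 events on BCD-085 kept apart from its placebo period.

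The cost is a few sentences in the SAP and Protocol, and no new data. Protocol 12.1 requires approval of any amendment that is not administrative before it takes effect, so the Protocol wording may need that step.

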8. ANALYSIS PLAN AND STATISTICAL METHODS

8.1. The software

Statistical processing of the data will be performed using R programming language for statistical computing and SAS 9.4 environment.

8.2. Description of the Statistical Methods to be Employed

The statistical analysis will be performed using two-sided hypothesis tests. The statistical significance level is 0.05.

The study hypothesis of non-inferior efficacy of BCD-085 once every 4 weeks vs. BCD-085 once every 2 weeks will be proved by comparing the lower bound of the 95% confidence interval for the difference in proportions of patients with PASI 75 at Week 12 between the BCD-085 Q4W and BCD-085 Q2W with pre-specified non-inferiority margin (δ) equal to -20.38%.

The hypothesis stating the superior efficacy of BCD-085 over placebo will be proved by comparing the lower bound of the 95% confidence interval for the difference in proportions of patients with PASI 75 by Week 12, in each BCD-085 arm and placebo arm, with pre-specified non-inferiority margin (δ , 0%).

Quantitative Data

The following quantitative data will be analyzed in the study:

Efficacy:

- Relative PASI change,
- Change in itch severity (VAS, 0 to 100 mm),
- Change in NAPSI score,
- Change in quality of life according to the DLQI score,

- Time to loss of PASI 75/90/100, sPGA 0-1/sPGA 0, DLQI 0-1 response during the treatment with BCD-085,

Safety:

- CBC results,
- Blood chemistry results,
- Vital signs,

Demographics and other baseline characteristics:

- General information (age, body weight, height, BMI),
- Duration of the disease, severity and the area of psoriasis (PASI), BSA, severity by sPGA, severity of nail psoriasis (NAPSI), severity of pruritus (VAS), quality of life score (DLQI), the presence of depression (Beck's score), functional activity (HAQ-DI), tender joint count (of 68), swollen joint count (of 66).

Quantitative data will be described using the following descriptive statistics: mean, SD, median, quartiles, CV, min, and max.

Quantitative variables will be tested for normality using the Shapiro-Wilk test.

Normally distributed quantitative variables will be tested using the two-sample Student's t-test, Welch's t-test, and ANOVA.

Non-normally distributed quantitative variables will be tested using the Mann-Whitney U-test, the Wilcoxon test, the Kruskal-Wallis test, and the Friedman test.

Time to loss of response will be assessed using log-rank test, Kaplan-Meier curves, and Cox regression model. Time will be counted from the response during the treatment with BCD-085. Right censoring can be used to analyze time to events.

Categorical Data

The following categorical data will be analyzed in the study:

Efficacy:

- Proportion of patients with PASI 75/90/100,
- Proportion of patients with sPGA score 0 or 1,
- Proportion of patients with DLQI score 0 or 1,
- Proportion of patients (among patients with psoriatic arthritis) who achieved an ACR20/50/70,
- Proportion of patients who maintained PASI 75/90/100 score,
- Proportion of patients who maintained sPGA score 0 or 1,

- Proportion of patients who maintained DLQI score 0 or 1,
- Proportion of patients who maintained ACR 20/50/70 response (among patients with psoriatic arthritis).

Safety:

- Proportion of patients who developed AEs/SAEs,
- Proportion of patients who developed injection site reactions,
- Proportion of patients who developed Grade 3/4 AEs/SAEs,
- Proportion of patients who discontinued the study due to AEs and/or SAEs,
- Exposure adjusted incidence rate of AEs/SAEs during the extension study.

Immunogenicity:

- Proportion of patients with anti-drug antibodies (binding/neutralizing).

Demographics and other baseline characteristics:

- General information (Race, Sex, Childbearing potential (women)),
- Prior therapies for plaque psoriasis,
- Co-morbidities and the most relevant prior diseases,
- Medical history.

Extent of exposure:

- The number of administrations given during the study,
- Exposure of BCD-085 with mean daily dose and treatment duration.

Percentages or proportions will be used to describe categorical data.

Categorical data will be processed using frequency tables, the Fisher's exact test, Yates-corrected Pearson's χ^2 test, and the Cochran-Mantel-Haenszel test.

The Benjamini-Yekutieli correction for multiple testing will be used.

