#### 4.3.3. Stratification procedure

In order to make the arms as balanced as possible, patients will be first stratified, and then randomized.

Stratification will be performed by the following:

- Body weight (< 100 kg/100 kg and more),
- Prior experience with monoclonal antibodies for the treatment of psoriasis (MAb-experienced/MAb-naive),
- PASI score (> 20/ $\geq$  20),
- Psoriatic arthritis (yes/no).

**Table 21.** Description of individual strata.

Stratum	Parameters
Stratum 1	

• Body weight below 100 kg

• The patient has never received monoclonal antibodies before

• PASI < 20

• Psoriatic arthritis: no

Stratum 2	

• Body weight below 100 kg

• The patient has never received monoclonal antibodies before

• PASI < 20

• Psoriatic arthritis: yes

Stratum 3	

• Body weight below 100 kg

• The patient has never received monoclonal antibodies before

• PASI <math>\geq</math> 20

• Psoriatic arthritis: no

Stratum	Parameters
Stratum 4	

• Body weight below 100 kg

• The patient has never received monoclonal antibodies before

• PASI <math>\geq</math> 20

• Psoriatic arthritis: yes

Stratum 5	

• Body weight below 100 kg

• The patient has never received monoclonal antibodies before

• PASI < 20

• Psoriatic arthritis: no

Stratum 6	

• Body weight below 100 kg

• The patient has never received monoclonal antibodies before

• PASI < 20

• Psoriatic arthritis: yes

Stratum 7	

• Body weight below 100 kg

• The patient has never received monoclonal antibodies before

• PASI <math>\geq</math> 20

• Psoriatic arthritis: no

Stratum 8	

• Body weight below 100 kg

• The patient has never received monoclonal antibodies before

• PASI <math>\geq</math> 20

• Psoriatic arthritis: yes

Stratum 9	

• Body weight below 100 kg

• The patient has received monoclonal antibodies before

• PASI < 20

• Psoriatic arthritis: no

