#### 4.3.4. Randomization procedure

Randomization in the study will be centralized. Patients will be randomly assigned to three arms at a 2:2:1 ratio.

Patients included in the study will be randomized within each stratum (block randomization). Thus, after stratification, the arms will be balanced by all specified characteristics.

Block randomization can be described as follows. The random sequence generator generates infinite random sequences consisting of the numbers from 1 to 18 (1,2,3,4,5,6,7,8,9,10,11,12,13,14,15,16,17,18). Each number (1 to 18) corresponds to one of 18 possible unique blocks (see the table below). As the study design does not define in advance the exact number of patients in each of the 32 strata, the patients will be randomized within each stratum to assure the equal distribution between the arms. Therefore, each stratum will contain its own block sequence (symbols “1”, “2”, and “3” corresponding to the 2:2:1 distribution).

Translated from Russian to English, dated 26-Nov-2019

**Table 22.** Examples of blocks for block randomization.

Block	Principle of assigning to treatment arms
#1	1,1,2,2,3
#2	1,2,1,2,3
#3	1,2,2,1,3
#4	1,2,2,3,1
#5	1,2,3,2,1
#6	1,3,2,2,1
#7	3,1,2,2,1
#8	2,2,1,1,3
#9	2,1,2,1,3
#10	2,1,1,2,3
#11	2,1,1,3,2
#12	2,1,3,1,2
#13	2,3,1,1,2
#14	3,1,1,2,2

Block	Principle of assigning to treatment arms
# 15	3,1,2,1,2
#16	3,2,1,1,2
#17	3,2,1,2,1
# 18	3,2,2,1,1

These blocks consist of the following symbols: “1”, “2” and “3”, and each of them corresponds to the study arms, for example, “1” to Arm 1, “2” to Arm 2, “3” to Arm 3.

Finally, a table is generated containing a random block sequence. Each stratum is assigned an infinite random sequence of blocks (an example is shown in 23).

**Table 23.** An example of assigning strata with block sequence.

Stratum	Sequence of blocks
Stratum 1	#1
	6
	5
	2
	...
Stratum 2	4
	3
	5
	#1
	...
Stratum 3	5

Stratum	Sequence of blocks
	5
	#1
	4
	...
...	...

During randomization, the BIOCAD's Clinical Study Manager allocates the patient to an appropriate stratum, assigns him/her the first free arm number in the block and a 3-digit randomization number coding this arm (corresponds to the patient's order number in the study). After randomization, the Clinical Study Manager assigns the patient an investigational product lot number (corresponding to the treatment arm) and a Patient ID. The investigator will know only the subject's ID and investigational product lot number.

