**Immunogenicity:**

- Proportion of patients with anti-drug antibodies (binding/neutralizing)

will be processed using the frequency tables, Fisher's test,  $\chi^2$  test, and Cochran-Mantel-Haenszel test. The categorical data will be described using percentages or proportions.

For multiple comparisons, the Benjamini-Yekutieli procedure will be used. Regression will be used to assess the effects of the factors other than the therapy type. Time to loss of response will be assessed using log-rank test, Kaplan-Meier curves, and Cox regression model. Time will be counted from the response during the treatment with BCD-085. Right censoring can be used to analyze time to events.

Statistical methods will be chosen based on the type and distribution of raw data. Applicability of certain statistical tests will be evaluated after all the data are collected because it is impossible to predict the distribution pattern, data homogeneity and other data characteristics in advance.

The data will be processed using programming language R for statistical processing and SAS 9.4 software environment.

Translated from Russian to English, dated 26-Nov-2019

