3. STUDY DESIGN

3.1 Design

The BCD-085-7 study is an international multicenter, randomized, double-blind, placebo-controlled clinical study to evaluate the efficacy and safety of two dosing regimens of BCD-085 (JSC BIOCADC, Russia) in patients with moderate to severe plaque psoriasis (Phase III).

The study is planned to enroll 213 adult patients with moderate to severe plaque psoriasis (diagnosed at least 6 months before signing the informed consent form) who have BSA $\geq 10\%$, PASI score ≥ 10 , and sPGA score ≥ 3 .

Before being screened for the study, patients must read and sign the informed consent form and undergo a screening examination (within 28 calendar days) to confirm that they are eligible for the study. The Protocol does not provide any additional requirements regarding the diet or physical activity during the screening or study period.

Stratification and randomization

When the Investigator has decided that the patient can take part in the study, the patient should be stratified according to his/her body weight (<100 kg/ ≥ 100 kg), previous use of monoclonal antibodies for the treatment of psoriasis (previously treated/naive), PASI score (<20 / ≥ 20), and psoriatic arthritis (yes/no) and randomized at a 2:2:1 ratio to one of the three study groups: 1) BCD-085 Q2W (Arm 1), 2) BCD-085 Q4W (Arm 2), 3) placebo (Arm 3).

Study periods

1. Screening (up to 28 days from signing the Patient Information Sheet with the Informed Consent Form, inclusive).
2. Main treatment period (from Week 0 through Week 54, inclusive).
3. Extension treatment period:
 - 1) for Arms 1 and 2: from Week 54 through Week 154,
 - 2) for Arm 3: from Week 54 through Week 166.
4. Follow-up period:
 - 1) for Arms 1 and 2: from Week 154 through Week 158,
 - 2) for Arm 3: from Week 166 through Week 170.

Screening period:

Up to 28 days from signing the Patient Information Sheet with the Informed Consent Form, inclusive.

Main treatment period (Week 0 through Week 54):

In this study period patients will be distributed to three arms:

- **Arm 1:** Patients in this arm (85 subjects) will receive BCD-085 120 mg (two subcutaneous injections, 60 mg in 1.0 mL each) once a week during the first 3 weeks (induction) and then once every 2 weeks through Week 10. Thus, the investigational product will be administered on Day 1 of Week 0, Week 1, Week 2, Week 4, Week 6, Week 8, and Week 10.

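### Cheap improvement, mainly for secondary endpoints: analyse change in itch VAS, NAPSI and DLQI by ANCOVA on the baseline score, and fix the contrast in advance instead of letting a normality test choose it

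*SAP*

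**What the plan says.** **Change endpoints.** SAP 8.2 lists change in itch VAS, NAPSI and DLQI among the quantitative data. It then states: "Quantitative variables will be tested for normality using the Shapiro-Wilk test". Variables judged normal go to Student's t, Welch's t or ANOVA; the others go to Mann-Whitney, Wilcoxon, Kruskal-Wallis or Friedman. No baseline covariate is mentioned, and ANCOVA appears in neither document. Protocol 9.1 adds that the applicability of tests will be judged once all data are in. Protocol 4.6.2 schedules all three scores at screening. Protocol 4.7.11 restricts NAPSI to patients with nail psoriasis at screening.

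**Primary endpoint.** For non-inferiority, SAP 8.2 prescribes "comparing the lower bound of the 95% confidence interval for the difference in proportions of patients with PASI 75 at Week 12" (Q4W minus Q2W), with a margin of -20.38%. It does not say how the interval is computed.

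**Randomization.** Protocol 4.3.4: "Patients included in the study will be randomized within each stratum (block randomization". The factors in Protocol 4.3.3 and SAP 3.1 are body weight, prior monoclonal antibody use, PASI score and psoriatic arthritis, each in two classes.

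**Adjustment methods that are named.** For categorical data, which include "Proportion of patients with PASI 75/90/100", the SAP 8.2 list ends with "test, and the Cochran-Mantel-Haenszel test", without strata. Protocol 9.1 says: "Regression will be used to assess the effects of the factors other than the therapy type". It names no endpoint, model or covariate, and the SAP does not repeat the sentence.

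**The concern.** A change score subtracts the whole baseline value. ANCOVA subtracts only the part that predicts the outcome, so the plain comparison of changes is usually noisier than it need be. The cost is precision on three secondary endpoints, and it is felt most for NAPSI, which has a reduced sample. The normality switch is a second problem: a difference in means and a rank contrast answer different questions, and the plan lets the data choose between them.

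For the primary interval, stratified blocks balance any prognostic factor between the arms, but a standard error that ignores the strata does not credit that balance. The interval is then slightly too wide, and an undefined interval method leaves a choice open at analysis.

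**Working it through.** **1. Change scores.** The inputs are not in the documents, so they are assumed and shown as ranges: q = follow-up SD / baseline SD, and ρ = baseline-outcome correlation. With baseline variance set to 1:

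- variance of change = 1 + q² - 2ρq
- ANCOVA residual variance = q²(1 - ρ²)
- difference between the two = (1 - ρq)², which is never negative, so in large samples with a common slope ANCOVA is never the less precise
- ratio ANCOVA / change = q²(1 - ρ²) / (1 + q² - 2ρq), which is (1 + ρ)/2 when q = 1

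Reduction in variance:

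| q | ρ = 0.2 | ρ = 0.5 | ρ = 0.7 |
|---|---|---|---|
| 0.75 | 57% | 48% | 44% |
| 1.00 | 40% | 25% | 15% |
| 1.25 | 27% | 11% | 2% |

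Example for the last cell: 1.5625 × 0.51 / (1 + 1.5625 - 1.75) = 0.7969 / 0.8125 = 0.981.

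At q = 1 the reductions are worth 1/0.60 = 1.67, 1/0.75 = 1.33 and 1/0.85 = 1.18 times the patients. All figures are against an unadjusted comparison of mean changes. None is claimed against the rank tests.

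**2. Primary interval: the plan's own figure.** Inputs from Protocol 9.3.1: 0.891 (Q2W), 0.826 (Q4W), margin -0.2038.

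- V = 0.891 × 0.109 + 0.826 × 0.174 = 0.240843
- distance to the margin = 0.2038 - 0.065 = 0.1388
- n per arm = V(z + 0.8416)² / 0.1388², which is 77.3 with z = 1.645 and 98.1 with z = 1.96

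The planned 77 per arm therefore reproduces at one-sided 5%. Under the two-sided 95% interval of SAP 8.2, power is Φ(0.1388/√(V/n) - 1.96):

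- n = 77: Φ(0.1388/0.0559 - 1.96) = 69.9%
- n = 85: Φ(0.1388/0.0532 - 1.96) = 74.1%

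This shortfall from 80% is a separate sample-size matter.

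**3. Primary interval: effect of stratifying.** Simulation of 200,000 trials with 2:2:1 blocks of 5 within 16 cells. Assumed prevalences are 30% for weight ≥100 kg, 20% for prior antibody use, 50% for PASI ≥20 and 25% for arthritis. Assumed log-odds effects on response are -1.2, -1.2, -0.4 and -0.4. An uncorrected Wald interval is compared with a Mantel-Haenszel risk difference (Sato variance) over the 4 weight-by-prior-antibody cells. Error is one-sided, at a true Q4W rate of 68.72%.

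| Per arm | Wald: error / power | 4-cell: error / power |
|---|---|---|
| 77 | 2.25% / 71.0% | 2.69% / 73.8% |
| 85 | 2.30% / 75.1% | 2.72% / 77.7% |

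- At equal actual error, power at 77 per arm is 72.6% for both.
- With no prognostic factor, power is 70.1% against 70.0% at 77 per arm.
- If only PASI class and arthritis (log-odds -1.2 each) are prognostic, it is 70.9% against 70.8%.
- With all 16 cells, error is 3.0-3.1%, and 86-89% of simulated trials had a cell with patients in only one active arm.

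**The case against.** **The plan does name stratified and regression methods.** This is true, and it would be too strong to infer that the plan ignores the randomization factors or excludes adjustment. What stands is narrower: neither method is tied to strata, to the decision interval or to the change endpoints.

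**A reader might infer that the unadjusted primary interval is invalid or biased.** The documents do not support that. The unadjusted difference is unbiased, and leaving out the strata errs, if at all, towards slight conservatism.

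**Stratifying the primary interval buys little.** This objection largely stands. The nominal gain comes with a higher error rate and disappears at equal error. The favourable scenario also gives the strong effects to the two pooled factors, and nothing in the documents ranks the four.

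**The Wald comparator is assumed.** This also stands. The sponsor's Phase II PASI 75 intervals (Protocol Table 12) reproduce as Wald with a continuity correction. For 24/30 against 6/26, 0.5692 ± (1.96 × 0.1103 + 0.0359) gives 31.72% to 82.13%. If that method were reused, exact unadjusted power would be 61.7% at 77 per arm and 67.3% at 85, with error of 1.6-1.7%. Most of any improvement would then come from dropping the correction. The documents do not say which method Phase III will use.

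**Rank tests may suit skewed, bounded scores.** This is fair. ANCOVA fixes a contrast of means even when scores are skewed, and no efficiency claim is made against ranks. The argument for settling the contrast in advance does not depend on that.

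**Conclusion.** The point holds as an improvement, not as a defect of validity. Its main part concerns itch VAS, NAPSI and DLQI. The baseline score is collected and unused, and the contrast is left to a normality test. The precision gain rests on the assumed SD ratio and correlation: 15-40% less variance at equal SDs for correlations of 0.2 to 0.7, more if follow-up scores vary less than baseline, and close to nothing (2%) at SD ratio 1.25 and correlation 0.7. The gain cannot be called large without knowing those values. Relative PASI change is not covered by these figures.

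The primary-interval part is minor. The interval method and strata are unspecified. A stratified interval mainly removes slight conservatism when the pooled factors are prognostic: about 3 points of nominal power, with one-sided error rising from about 2.2% to 2.7%. It would be tempting to read this as a cure for the planned sample size. It is not: even in the favourable scenario power stays at 73.8% (77 per arm) or 77.7% (85 per arm).

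**What to change.** 1. In SAP 8.2, analyse change in itch VAS, NAPSI and DLQI by ANCOVA with arm, baseline score and the four stratification factors as main effects. Restrict NAPSI to patients with nail psoriasis at screening. Remove the Shapiro-Wilk switch for these endpoints.
2. Name the method for the primary 95% interval. Optionally, pre-specify beside the unadjusted interval a supportive risk-difference interval that accounts for the randomization factors, for example Mantel-Haenszel with Sato variance over a few pooled cells. Do not use all 16. The supportive interval should not replace the unadjusted one in the decision.

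**Timing.** Codes are opened at Visit 8 (Protocol 4.3.5), and Protocol 4.6.1 already provides for patients who have finished the main period. Sign off before any Week 12 comparison by arm; otherwise label the new analyses as sensitivity analyses.

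**Cost.** No new data and slightly more programming. The reported contrast is on means even for skewed scores.
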